### **2.3 Exploratory Objectives**

1. To investigate the association between treatment outcome and expression of programmed cell death-ligand (PD-L1) in archived NPC tissues
2. To explore the relationship between response to treatment (ORR, PFS, and overall survival OS) and TGF- $\beta$ 1
3. To explore the relationship between response to treatment (ORR, PFS, and overall survival OS) and the profile of exosomal PD-L1

### **2.4 Study Design**

This is a prospective phase II, single arm clinical trial conducted in Queen Mary Hospital (Hong Kong) assessing the efficacy and safety of bintrafusp alfa in previously treated recurrent / metastatic nasopharyngeal cancer patients.

## 2.5 Study Participants

A total of 38 patients will be accrued to assess the potential benefit of bintrafusp alfa.

# 3 ELIGIBILITY CRITERIA

## 3.1 Inclusion Criteria

[figure not shown]
1. Histologically or cytologically confirmed non-keratinizing differentiated (World Health Organization WHO Type II) or undifferentiated (WHO Type III) nasopharyngeal carcinoma (NPC) that has recurred at regional or / and distant sites
2. Measurable disease according to the RECIST criteria (version 1.1) for the evaluation of measurable disease
3. Received one or more lines of chemotherapy, which must include prior treatment with a platinum agent either
  - a. For the treatment of metastatic or recurrent disease
  - b. Experienced progression of disease within 6 months following completion of a platinum-based combination therapy as part of (neo)-adjuvant therapy
4. Male or female subjects with age: 18-79 years old
5. Eastern Cooperative Oncology Group (ECOG) performance status of 0, 1 or 2
6. No prior immunotherapy
7. Written informed consent obtained for clinical trial participation and providing archival tumor tissue, if available
8. Females of childbearing potential or non-sterilized male who are sexually active must use a highly effective method of contraception
9. Females of childbearing potential must have negative serum or urine pregnancy test
10. Have life expectancy  $\geq 3$  months
11. Adequate organ function as defined as:
  - a. Absolute neutrophil count  $\geq 1.5 \times 10^9/L$
  - b. Platelet count  $\geq 100 \times 10^9/L$
  - c. Hemoglobin  $\geq 8.0 \text{ g/dL}$
  - d. Serum alanine aminotransferase ([ALT]; serum glutamate-pyruvate transferase [SGPT]), or serum aspartate aminotransferase [AST] where available at the center)  $< 2.5 \times$  upper limit of normal (ULN), OR  $< 5 \times$  ULN in the presence of liver metastases
  - e. Serum total bilirubin  $< 2 \times$  ULN
  - f. Serum creatinine  $< 1.5 \times$  ULN

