### **Clinical Evidence for anti-PD1 / anti-PD L1 Therapy in NPC**

KEYNOTE-028 (NCT02054806) is a non-randomized, multi-cohort, phase Ib trial of Pembrolizumab in patients with PD-L1-positive advanced solid tumors. PD-L1 positivity, defined as PD-L1 expression by immunohistochemistry (IHC) ( $\geq 1\%$  PD-L1 membrane staining of tumor cells or tumor-infiltrating lymphocytes), was required for the study entry. The key eligibility criteria of NPC cohort was unresectable or metastatic NPC patients who are not amendable to curative treatment whose disease progressed on at least one line of prior therapies. (21)

Enrolled subjects were predominantly of Asian ethnicity (67%), male (77.8%), with an Eastern Cooperative Oncology Group (ECOG) performance status of 1 (74%). Of note, approximately two-thirds had received 3 or more prior treatments for metastatic disease. All patients had received prior platinum-based therapy. 98% of screened and 100% of evaluable subjects were PD-L1 positive. In this heavily pre-treated cohort, evidence of clinical activity was demonstrated, as 22.2% had a confirmed ORR, 25.9% had unconfirmed response, and 51.9% had stable disease (SD). With a median follow-up of 7.8 months, the 6-month and 12-month progression free survival (PFS) rate was 49.7% and 30.1% respectively. Notably, a 6-month and 12-month overall survival (OS) rate was 85.2% and 66.7% demonstrated respectively. Grade 3  $\geq$  drug-related adverse events occurred in 29.6% of patients, and there was one drug-related death due to sepsis.

NCI-9742 is an international, multi-center study of Nivolumab in recurrent or metastatic NPC. (22) Similar population of advanced or metastatic NPC patients who are not amendable to curative treatment whose disease progressed on at least one line of platinum therapies was enrolled. However, PD-L1 positivity is not the mandatory eligibility requirement.

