## 3.2 Exclusion Criteria

1. Prior invasive malignancy within 2 years except for non-invasive malignancies such as cervical carcinoma in situ, in situ prostate cancer, non-melanomatous carcinoma of the skin, lobular or ductal carcinoma in situ of the breast that has been surgically cured
2. Isolated local recurrence or persistent disease
3. Has disease that is suitable for local therapy administrated with curative intent

4. Severe, active co-morbidity
5. Currently participating in and receiving clinical trial treatment or has participated in a trial of an investigational agent and received study treatment or used an investigational device within 4 weeks of the first dose of treatment
6. Has prior chemotherapy, targeted therapy, or radiation therapy within 2 weeks prior to study Day 1 or who has not recovered ( $\leq$  grade 1 or at baseline) from adverse events due to previous administered agent
7. Untreated active central nervous system (CNS) metastatic disease, lepto-meningeal disease, or cord compression
8. Clinically significant (active) cardiovascular disease: cerebral vascular accident/stroke ( $<6$  months prior to enrollment), myocardial infarction ( $<6$  months prior to enrollment), unstable angina, congestive heart failure ( $\geq$  New York Heart Association Classification Class II), or serious cardiac arrhythmia requiring medication.
9. Prior treatment with any other anti-programmed cell death protein-1 (anti-PD-1), or PD Ligand-1 (PD-L1) or PD Ligand-2 (PD-L2) agent or an antibody targeting other immuno-regulatory receptors or mechanisms
10. Irritable bowel syndrome or other serious gastrointestinal chronic conditions associated with diarrhea within the past 3 years prior to the start of treatment
11. Known history of testing positive for HIV or known acquired immunodeficiency syndrome.
12. On chronic systemic steroid or any other forms of immunosuppressive medication within 14 days prior to the treatment. Except:
  - a. Intra-nasal, inhaled, topical steroids, or local steroid injection (e.g., intraarticular injection);
  - b. Systemic corticosteroids at physiologic doses  $\leq 10$  mg/day of prednisone or equivalent;
  - c. Steroids as premedication for hypersensitivity reactions due to bintrafusp alfa
13. Active or prior documented autoimmune or inflammatory disorders in the past 2 years, except diabetes type I, vitiligo, psoriasis, or hypo- or hyperthyroid diseases not requiring immunosuppressive treatment

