### 7.2 Sample Size Calculation

H0: The null hypothesis is that the overall response rate (ORR) is similar to historical result of immunotherapy, i.e. 20%

H1: The alternative hypothesis of treatment efficacy: experimental treatment with bintrafusp alfa would result in 40% ORR.

To detect 20% of differences from 20% to 40% in the number of patients proceeding to surgery, with Type I error of 0.05 and 80% power, the target sample size is 33 patients.

Modified Simon's two-stage optimal design will be used. In the first stage, 18 patients will be enrolled. If there are 4 or fewer responses in these 18 patients, the study will be stopped. Otherwise, 15 additional patients will be accrued for a total of 33 valid cases. The null hypothesis will be rejected if 11 or more responses are observed in 33 patients and the treatment will be considered worthy of further investigation. Patients may drop out before their objective response can be assessed. Such patients will be excluded for the ORR assessment and will be replaced by other patients that the objective response can be assessed. The study will be continued until the first or the second stage evaluation is achieved. Assuming 10% drop out rate, 38 patients will be accrued initially. We assume 50% of screened population will be eligible for the study, thus we plan to screen for 76 patients.

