- f. Hematology parameters include the following laboratory tests: complete blood count with 3-part differential (i.e. total neutrophil count including bands, lymphocytes, and monocytes), hemoglobin, hematocrit and platelets.
- g. Blood chemistry must include glucose, BUN, creatinine (eGFR), sodium, potassium, magnesium, chloride, calcium, CO2, alkaline phosphate, AST (SGOT), total bilirubin, total protein, albumin, phosphorus, uric acid.
- h. Coagulation test include PT, PTT and INR.
- i. Plasma EBV DNA will be determined before treatment and every 2 weeks until disease progression; plasma TGF $\beta$ 1 measurement will be performed every 8 weeks until disease progression; PD-L1 concentration in the exosome will be measured every 2 weeks until disease progression.
- j. Pregnancy test will be performed within 1 week prior to treatment, if a cycle is missed during treatment or pregnancy and at the end of treatment visit only for women of childbearing potential.
- k. Patients will have CT scan at Screening/Baseline ( $\leq$  28 days prior to initiation of trial treatment), every 8 weeks for the first 12 months, and every 12 weeks thereafter. Patients will also have CT scan whenever disease progression is suspected. For patients who discontinue treatment without radiographic progression per RECIST 1.1 (e.g. in patients who discontinue treatment for clinical progression or adverse reactions), disease assessment should continue as stated in schedule until radiographic disease progression or alternate therapy is given.
- l. Quality of life (QoL) will be assessed by patient-reported EORTC QLQ-C30 and H&N-35 questionnaires every 12 weeks in the first year.
- m. If screening assessments were completed within 28 days, they do not need to be repeated on Day 1 of Cycle 1 if patient's condition has not changed.

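### Inclusion criterion 3a does not require progression, although the cohorts that appear to supply the 20% null had all progressed, so shrinkage from earlier chemotherapy can count as response

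*Protocol*

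**What the plan says.** Protocol Section 3.1, criterion 3, asks for at least one line of chemotherapy including a platinum agent, by either of two routes:

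- 3a: "For the treatment of metastatic or recurrent disease".
- 3b: "Experienced progression of disease within 6 months following completion of a platinum-based combination therapy as part of (neo)-adjuvant therapy".

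Criterion 1 asks for disease "that has recurred at regional or / and distant sites", and criterion 2 for measurable disease. On timing, exclusion 6 in Section 3.2 rules out a patient who "Has prior chemotherapy, targeted therapy, or radiation therapy within 2 weeks prior to study Day 1", or who has not recovered from the adverse events of earlier treatment. The Section 11 footnote on CT places the baseline scan at most "28 days prior to initiation of trial treatment), every 8 weeks for the first 12 months".

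Section 7.2 states: "The null hypothesis is that the overall response rate (ORR) is similar to historical result of immunotherapy, i.e. 20"%. The alternative is 40%. The trial stops if 4 or fewer of 18 patients respond, and the null is rejected if 11 or more of 33 respond. The only response rates for immunotherapy in this disease are in Section 1: 22.2% in the pembrolizumab phase Ib cohort (patients "whose disease progressed on at least one line of prior therapies") and 20.5%, or 9 of 44, in the nivolumab study (patients "whose disease progressed on at least one line of platinum therapies was enrolled").

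**The concern.** Progression is written into one route and absent from the other, and nothing else supplies it. Criterion 1 can be met by the very recurrence for which the platinum was given. Criterion 2 can be met by residual lesions in stable disease or partial response. Exclusion 2 reads as concerning isolated local disease and does not close the gap.

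As written, a patient who finished first-line platinum just over two weeks earlier, without having progressed, can be registered. The trial has one arm, and its primary endpoint is investigator-assessed ORR against a fixed 20%. No control group would show how much of an observed response belongs to the previous regimen. At stake is whether 11 responses in 33 patients can be read as activity beyond anti-PD-1 therapy.

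**Working it through.** **1. Reproduce the design.** Inputs from Section 7.2: first stage 18 patients, stop at 4 or fewer responses; second stage 15 more; reject at 11 or more of 33. For a true response rate p,

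P(reject) = Σ over x = 5 to 18 of P[Bin(18, p) = x] × P[Bin(15, p) ≥ 11 − x].

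- p = 0.20: 0.0458
- p = 0.40: 0.801

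This agrees with the stated 0.05 (one-sided) and 80% power. The sample-size arithmetic is not at fault.

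**2. Is there a route for carry-over?** The baseline CT may be taken on Day −28, and chemotherapy is barred only within 2 weeks of Day 1. A cycle given between the scan and about Day −15 is therefore permitted, and the shrinkage it causes is measured from that scan. Footnote m of the schedule says screening assessments done within 28 days need not be repeated at Cycle 1 if the patient's condition has not changed. A patient whose chemotherapy ended before the scan may also still be shrinking afterwards.

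**3. Scenario calculation.** Assumptions, neither in the protocol: a share f of evaluable patients entered without progression and shows an apparent ORR of q; all others respond at 20%, so the drug is no better than the null. Then p = 0.20(1 − f) + qf. Example: f = 0.20 and q = 0.40 give p = 0.16 + 0.08 = 0.24.

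P(reject), with p in brackets:

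| q | f = 10% | f = 20% | f = 30% |
|---|---|---|---|
| 10% | 3.3% (0.19) | 2.3% (0.18) | 1.5% (0.17) |
| 20% | 4.6% (0.20) | 4.6% (0.20) | 4.6% (0.20) |
| 30% | 6.2% (0.21) | 8.2% (0.22) | 10.6% (0.23) |
| 40% | 8.2% (0.22) | 13.4% (0.24) | 20.1% (0.26) |
| 50% | 10.6% (0.23) | 20.1% (0.26) | 32.6% (0.29) |

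Of 33 patients, 10% is about 3 and 30% about 10. With f = 0 the value stays at 4.6%.

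**The case against.** **The direction is not settled.** Response is measured from a new baseline. A patient already in partial response must shrink substantially again from a smaller tumour burden, and a plateau does not count. So q could lie at or below 20%, and the top rows of the table show the error rate then falling or unchanged. This stands: the effect may go either way. What remains is that carry-over is a specific upward route that the eligibility and timing rules leave open.

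**The effect may be small.** If only about 3 of 33 patients are affected, the figures for q of 30–50% are 6.2–10.6%. For comparison, a true rate of 22.2%, the pembrolizumab cohort's own figure, already gives 8.7%. This also stands, and it limits the severity.

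**Progression may have been intended.** Section 1 describes the setting as patients refractory to cisplatin-based regimens or failing first-line platinum. But the study hypothesis and objectives speak of previously treated patients, and Section 4.2 has registration check the criteria as written. Probable intent makes the repair easy; it does not supply the missing condition.

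**The source of the null is inferred.** Section 7.2 does not name the cohorts. They are, however, the only immunotherapy results in this disease that the protocol reports.

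**A stronger reading to avoid.** A reader might infer that non-progressed patients have a better prognosis and would therefore respond more often. Nothing in the protocol links non-progression to a higher response rate, and the point does not need it.

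**Conclusion.** The point holds as a mismatch between criterion 3a and the population that appears to stand behind the 20% null, made more consequential by a chemotherapy-free interval shorter than the baseline scan window. The error rate of the primary test is then uncalibrated: across the assumed scenarios it runs from 1.5% to 32.6% against a nominal 4.6%, with upward bias through carry-over the concern.

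A reader might take the upper figure as the trial's actual false-positive rate. The protocol does not support that. It gives neither f nor q, so the table is a scenario range and not an estimate. Nor does it show that any non-progressed patient was enrolled.

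It would also be too strong to say that requiring progression makes the population match. The historical cohorts had progressed on at least one prior line, not necessarily the latest. About two-thirds (pembrolizumab) and 60% (nivolumab) had three or more prior treatments, against one or more here, and the pembrolizumab cohort was selected for PD-L1 positivity. The amended 3a would not mirror 3b either, which carries a 6-month limit.

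Severity: should be fixed. Confidence: moderate.

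**What to change.** 1. Add to 3a documented disease progression on or after prior therapy, naming either the platinum-containing regimen or the most recent systemic therapy. The latter closes the carry-over route more completely but is stricter than the historical cohorts' condition; the former is nearer to it.
2. Require the baseline scan to be taken after the last dose of prior chemotherapy, so that the exclusion 6 interval and the 28-day scan window are reconciled.
3. If anyone has already entered through 3a without progression, report ORR without those patients beside the primary result. This needs progression status at entry to be recorded.

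The cost is a short amendment, some rescheduling of baseline scans, and a wait for the few patients who stopped platinum without progressing. N = 33 and the 4/18 and 11/33 rules do not change. Differences in prior lines and PD-L1 selection remain and should be acknowledged when the result is set against 20%.

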## 3.2 Exclusion Criteria

1. Prior invasive malignancy within 2 years except for non-invasive malignancies such as cervical carcinoma in situ, in situ prostate cancer, non-melanomatous carcinoma of the skin, lobular or ductal carcinoma in situ of the breast that has been surgically cured
2. Isolated local recurrence or persistent disease
3. Has disease that is suitable for local therapy administrated with curative intent

4. Severe, active co-morbidity
5. Currently participating in and receiving clinical trial treatment or has participated in a trial of an investigational agent and received study treatment or used an investigational device within 4 weeks of the first dose of treatment
6. Has prior chemotherapy, targeted therapy, or radiation therapy within 2 weeks prior to study Day 1 or who has not recovered ( $\leq$  grade 1 or at baseline) from adverse events due to previous administered agent
7. Untreated active central nervous system (CNS) metastatic disease, lepto-meningeal disease, or cord compression
8. Clinically significant (active) cardiovascular disease: cerebral vascular accident/stroke ( $<6$  months prior to enrollment), myocardial infarction ( $<6$  months prior to enrollment), unstable angina, congestive heart failure ( $\geq$  New York Heart Association Classification Class II), or serious cardiac arrhythmia requiring medication.
9. Prior treatment with any other anti-programmed cell death protein-1 (anti-PD-1), or PD Ligand-1 (PD-L1) or PD Ligand-2 (PD-L2) agent or an antibody targeting other immuno-regulatory receptors or mechanisms
10. Irritable bowel syndrome or other serious gastrointestinal chronic conditions associated with diarrhea within the past 3 years prior to the start of treatment
11. Known history of testing positive for HIV or known acquired immunodeficiency syndrome.
12. On chronic systemic steroid or any other forms of immunosuppressive medication within 14 days prior to the treatment. Except:
  - a. Intra-nasal, inhaled, topical steroids, or local steroid injection (e.g., intraarticular injection);
  - b. Systemic corticosteroids at physiologic doses  $\leq 10$  mg/day of prednisone or equivalent;
  - c. Steroids as premedication for hypersensitivity reactions due to bintrafusp alfa
13. Active or prior documented autoimmune or inflammatory disorders in the past 2 years, except diabetes type I, vitiligo, psoriasis, or hypo- or hyperthyroid diseases not requiring immunosuppressive treatment
14. Known active hepatitis B or known hepatitis C is detected; subjects who have been treated and now have an undetectable viral load are eligible
15. History of primary immunodeficiency or solid organ transplantation
16. Receipt of live, attenuated vaccine within 28 days prior to the study treatment
17. Active infection requiring systemic therapy
18. Severe hypersensitivity reaction to treatment with another monoclonal antibody (mAb)
19. Females who are pregnant, lactating, or intend to become pregnant during their participation in the study
20. Psychiatric disorders and substance (drug/alcohol) abuse

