## **6 FOLLOW UP AND OUTCOME EVALUATION**

### **6.1 Follow-Up Schedule**

All participants will be followed every 2 weeks during the intervention. At each visit, patient's performance status and toxicity of treatment will be monitored, and blood test will be checked for complete blood count, liver function, and renal function. Thyroid function test and early morning cortisol (9am) will be performed at least every 4 weeks while on bintrafusp alfa therapy. For female patients in reproductive age, urine or serum pregnancy test needs to be performed at least every month while the subject is on bintrafusp alfa therapy. All adverse events and laboratory abnormalities will be graded per the National Cancer Institute Common Terminology Criteria for Adverse Events, version 4.0.

For blood-borne immune markers and exploratory biomarkers, plasma EBV DNA will be determined before treatment and every 2 weeks until disease progression; plasma TGF $\beta$ 1 measurement will be performed every 8 weeks until disease progression; exo-PD-L1 concentration will be measured every 2 weeks until disease progression.

Tumor imaging by CT head, neck, chest, abdomen, and pelvis will be done at baseline, every 8 weeks for the first 12 months, then every 12 weeks thereafter. Response will be assessed per RECIST version 1.1. Treatment decisions will be based on Investigator(s) review.

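### The baseline CT may be up to 28 days old while prior anticancer therapy is barred only for the last 2 weeks, so shrinkage from earlier treatment can be counted in the single-arm ORR

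*Protocol*

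**What the plan says.** Four parts of the protocol bear on this.

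- **Washout.** Section 3.2, exclusion 6, excludes a patient who "Has prior chemotherapy, targeted therapy, or radiation therapy within 2 weeks prior to study Day 1", or who has not recovered from the adverse events of earlier agents. Therapy that ended before those 2 weeks is allowed.
- **Age of the baseline scan.** Footnote k of the Schedule of Assessments (section 11) sets the screening CT at no more than "28 days prior to initiation of trial treatment), every 8 weeks for the first 12 months, and every 12 weeks thereafter". Section 6.1 gives the same rhythm: imaging "will be done at baseline, every 8 weeks for the first 12 months, then every 12 weeks thereafter".
- **Cycle 1 Day 1.** The CT row of the schedule appears to carry a mark at Cycle 1 Day 1 as well as at screening. Footnote m, however, says of screening assessments completed within 28 days that "they do not need to be repeated on Day 1 of Cycle 1 if patient's condition has not changed". It does not mention anticancer therapy given between the scan and Day 1.
- **Endpoint and test.** Section 6.2 defines ORR as investigator-assessed complete or partial response by RECIST 1.1. Section 7.2 tests it in one arm against 20%: stop at 4 or fewer responses in 18, reject at 11 or more in 33.

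No section requires the baseline CT to come after the last dose or fraction of prior therapy.

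**The concern.** RECIST response is measured as change from the baseline scan. If chemotherapy or radiotherapy is given after that scan, its effect lies inside the measured interval and is indistinguishable from the effect of bintrafusp alfa at the Week 8 scan. A randomised comparison would carry such an effect in both arms. Here there is one arm and a fixed 20%, so every misattributed response goes straight into the primary endpoint and toward rejecting the null hypothesis. The analysis stage cannot repair this, because it cannot supply a baseline scan that was never taken.

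**Working it through.** **Step 1: the overlap.** Oldest permitted baseline CT: 28 days before first dose (footnote k). Latest permitted prior therapy: about 14 days before Day 1 (exclusion 6). Difference: 28 − 14 = 14 days. For example, a scan on Day −28, prior therapy ending about Day −15 and first dose on Day 1 meets both rules. Whether the Day −28 scan may stand as baseline then depends on how the condition in footnote m is read. A patient who is clinically stable while lesions shrink could be judged unchanged.

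**Step 2: the plan's own figure.** For a counted response rate p, the probability of rejecting the null hypothesis is

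R(p) = Σ (x = 5 to 18) P[Bin(18, p) = x] × P[Bin(15, p) ≥ 11 − x].

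- R(0.20) = 0.046, against the stated 0.05.
- R(0.40) = 0.801, against the stated 80%.

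The design reproduces, and nothing in this point questions it.

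**Step 3: sensitivity to carry-over.** Let f be the share of patients with therapy after their baseline scan, and q the share of their non-responses that are counted as responses. With a true ORR of 20%, the counted rate is

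p = 0.20 + 0.80 × f × q.

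The protocol gives neither f nor q. Both are assumptions, with q held at 20%.

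| f | q | Counted ORR | Type I error R(p) |
|---|---|---|---|
| 0 | – | 20.0% | 0.046 |
| 2% | 20% | 0.20 + 0.80 × 0.02 × 0.20 = 20.3% | 0.051 |
| 5% | 20% | 0.20 + 0.80 × 0.05 × 0.20 = 20.8% | 0.059 |
| 10% | 20% | 0.20 + 0.80 × 0.10 × 0.20 = 21.6% | 0.074 |
| 20% | 20% | 0.20 + 0.80 × 0.20 × 0.20 = 23.2% | 0.111 |

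**Step 4: scale in patients.** One extra false response per 33 patients on average gives p = 0.20 + 1/33 = 23.0% and R(p) = 0.107. Few misattributed responses are needed to matter, but the table shows that a rare overlap barely moves the error rate.

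**The case against.** The strongest case against is that the sequence is narrow and partly guarded.

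- A Cycle 1 Day 1 CT appears to be scheduled, and the waiver is conditional. A further chemotherapy cycle after the scan could well be seen as a change in the patient's condition. This stands in part: the wording can be read that way but does not say so, and a site reading it the other way breaks no rule.
- Consent must be within 28 days of first dose and must precede study activities. A trial-specific early scan would therefore mean further prior therapy after consent; otherwise a routine scan is reused. Recovery from toxicity and the blood-count limits narrow the group further. This stands, and it argues for small values of f.
- In a patient who receives nothing after an early scan, growth before Day 1 counts against the study drug. This also stands: the net direction across all patients is not established. The calculation covers the carry-over component only.

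A reader might go further in three directions that the protocol does not support.

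- **That the 20% null comes from patients who had progressed on their latest therapy.** The Background describes the pembrolizumab cohort as patients "whose disease progressed on at least one line of prior therapies", and the nivolumab study as progression on at least one platinum line. Neither description says the most recent line. The scan and washout windows of those studies are not given either, so similar carry-over may already be within the 20%.
- **That recently irradiated lesions are uncontrolled as target lesions.** Measurable disease follows RECIST 1.1 by reference, so a gap cannot be shown from this document.
- **That the EBV DNA baseline has the same defect.** The biomarker row also appears to carry a Cycle 1 Day 1 sample, so this is at most a weak extension.

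**Conclusion.** The point holds as a permissive window that should be tightened. The protocol allows up to about 14 days of active prior treatment after the RECIST baseline, and the only safeguard, the Cycle 1 Day 1 scan, can be waived on a condition that does not mention intervening therapy. With q assumed at 20%, the type I error moves from 0.046 to between 0.051 (f = 2%) and 0.111 (f = 20%). A reader might infer from the upper figure that the trial's false-positive rate is in fact doubled. The documents do not support that: they show that misattribution is permitted, not how often it would happen. The sample size and decision rule are correct as stated.

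Inclusion 3a is a separate matter. It asks for platinum "For the treatment of metastatic or recurrent disease" without requiring progression, while 3b does require it and the historical populations are described as having progressed on at least one line. That question of population definition would remain even if every baseline CT were taken on Day 1, and it does not raise the severity of the scan-timing point.

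Severity: should-fix.

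**What to change.** In footnotes k and m:

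1. Require the baseline CT to be obtained after the last dose or fraction of any prior anticancer therapy and within 28 days before Day 1.
2. State that the footnote m waiver does not apply to the CT if anticancer therapy was given after the screening scan. The Cycle 1 Day 1 CT already in the schedule then serves as baseline.

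Separately, reconcile inclusion 3a with the Background's description of the populations behind the 20% null, or explain why the difference is acceptable.

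The cost is a short amendment and a few scans retimed or repeated. The washout length and the treatment rules stay as they are. The change reduces carry-over but does not remove it: a scan taken soon after the last prior dose can still be followed by delayed shrinkage from that therapy.
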